8.1 Responsibility for data and safety monitoring

[name] will be responsible for monitoring the trial.

8.2 Frequency of DSM reviews

Data will be reviewed in the course of the trial on a quarterly basis. A full DSM report will be generated annually.

8.3 Content of DSM report

The content of the annual DSM report will follow this structure: (1) Brief description of the trial, (2) Baseline sociodemographic characteristics, (3) Retention and disposition of study participants, (4) Q.A. issues, (5) Regulatory issues, (6) AEs, (7) SAEs, (8) Efficacy. A copy of this report will be provided to the NIDA project officer annually.

9 DSM Board Plan

[figure not shown]
A DSMB is not needed for this low-risk, single-site trial of two behavioral interventions for smoking cessation.

References

3. Dillman DA. *Mail and Internet Surveys: The Tailored Design Method*. 2nd ed. Hoboken, NH: John Wiley & Sons, Inc.; 2007.

Appendix B: Fraud Prevention Protocol

ANTI-FRAUD PROCEDURES FOR STUDY ENTRY

ANTI-FRAUD PROCEDURES FOR POST-ENROLLMENT DATA CLEANING

Procedure for project manager to validate eligibility post-enrollment:

1. Datatope will create post-enrollment flags on data validity, including (a) inconsistency between outcome surveys and screening/baseline surveys in date of birth, (b) multiple IP addresses/non-US IP addresses detected post-enrollment
2. Post-baseline manual checks for address and IP address.
3. Depending on level of evidence for fraud a participant could be flagged and contacted by telephone. Let them know that, before they can be compensated for their participation, we need to verify that some of the information that they provided is correct.
4. Ask for full name and address. If different than what they provided previously, ask if they may have provided any other name or address and the reason for the change.
5. Ask for their date of birth, current age, gender, and race and ethnicity. If gender or race/ethnicity are different than what they provided previously, ask if they may have provided any different response on a survey.
6. After completing the call, check information provided against survey data. If there is clear evidence of deception (e.g, different dates of birth provided, non-matching age and DOB, different first and last name provided across surveys, with no explanation), note in their study record that they should be excluded from outcome analyses. Do not mail compensation for survey completion if they can't be reached for verification.
7. After final dataset is received from Datatope, review all records for incoherent responses to open-ended questions on baseline & follow-up surveys. Flag these records for manual review to check for data quality (e.g, evidence of straightlining, unusual responses).
8. In cases where deception is suspected but cannot be confirmed, add participant ID to database of participants whose inclusion will be adjudicated by the study team prior to analyzing outcome data. Include note providing all reasons why deception is suspected, along with any evidence that might indicate that the participant's data are valid.

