4.2.3 Procedures during data analysis

When data collection is complete, the study statistician will lock the database and conduct quality checks. Data quality will be assessed through a number of analytic methods. The study statistician will tabulate categorical variables with frequency counts, and for continuous variables we will examine descriptive statistics (mean, standard deviation, median, interquartile range, minimum, maximum), distributional characteristics (skewness, kurtosis, frequency histograms, normal probability plots), and associations (correlations, scatter plots). Any free text or numeric values will be checked for accuracy, range consistency, and outlying values. We will examine all missing response data to determine whether or not there are predictive characteristics that suggest the values are not missing at random and to determine whether imputation may be needed. Data determined to be invalid based on apparent inaccuracies (e.g., two different dates of birth provided at different survey time points) that cannot be resolved via follow-up with participants will be excluded from the final dataset.

5 Regulatory issues

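### Appendix B steps 7-8 let the study team exclude suspected-fraud cases after follow-up survey text has been read, with no masking specified and no analysis that retains those records

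*Combined protocol and SAP*

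**What the plan says.** Appendix B (anti-fraud procedures for post-enrollment data cleaning) gives two routes out of the analysis.

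- **Step 6.** After a verification call, the record of a participant with a clear identity mismatch gets a "note in their study record that they should be excluded from outcome analyses" entry. The examples concern date of birth, age and name.
- **Steps 7-8.** After the final dataset is delivered, the instruction is to "review all records for incoherent responses to open-ended questions on baseline & follow-up surveys". Records flagged in this way go to manual review, where the examples of what to look for are "evidence of straightlining, unusual responses". Participants with suspected but unproven deception join a list "whose inclusion will be adjudicated by the study team prior to analyzing outcome data", with a note of the reasons for suspicion and of any evidence that the data are valid.

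No threshold is given for steps 7-8, and nothing is said about masking. The only masking statement, in section 14.4, covers outcome evaluators who deal directly with participants.

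Section 4.2.3 of the Data & Safety Monitoring Plan (Appendix A) adds that invalid data which "cannot be resolved via follow-up with participants will be excluded from the final dataset"; its example is two conflicting dates of birth.

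Section 14.2 specifies a modified intent-to-treat set (opened the app at least once). Its sensitivity analyses cover concomitant treatment, complete cases and multiple imputation. Neither section 14.2 nor DSMP section 7.2 mentions fraud exclusions.

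**The concern.** Steps 7-8 create a discretionary exclusion after randomisation. The survey that supplies the open text also carries the endpoints: Table 1 in section 8.1 puts satisfaction, tobacco use, BADS and PHQ-8 on the 8-week survey, and satisfaction is a primary endpoint. A judgement on whether a doubtful record stays in could therefore be made with that participant's arm and answers in view.

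The timing clause in step 8 deals with one risk, namely deciding after seeing which way the arms differ. It does not deal with the other, which is deciding on a single record while knowing its arm or its outcome.

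The trial is an unpowered pilot whose stated purpose is a preliminary effect-size estimate for a later full-scale application (section 14.3). With few abstainers expected, a handful of records can move that estimate. The planned analyses would not show that this had happened.

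**Working it through.** **Who decides, what they can see, and when**

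1. The adjudicator is the study team. Section 8.2 has the study team send each participant the message with the link to the assigned app, so access to arm is plausible, though not stated.
2. The reviewed material includes follow-up open text. Section 8.3 says the follow-up questions probe app content and push notifications, and the comparison table in section 7.2 shows that these differ between arms. That the text identifies the arm is plausible but not shown.
3. The decision falls after delivery of the dataset and before outcome analysis. Nothing says that arm or endpoint fields are withheld.

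**Sample size.** This is the only plan figure involved: 60 per arm per stratum × 2 strata × 2 arms = 240, or 120 per arm (section 14.3). It reproduces. The plan gives no power calculation and no expected number of exclusions.

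**Abstinence illustration.** Inputs: n = 120 per arm; rates of 13% and 8% borrowed from the earlier SmartQuit versus QuitGuide pilot (section 2.2.3), so 0.13 × 120 = 15.6 ≈ 16 and 0.08 × 120 = 9.6 ≈ 10 abstainers. Missing counts as non-abstinent, so the denominators stay at 120 before exclusions. The number removed, k, is assumed.

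Base: 16/120 − 10/120 = 13.3% − 8.3% = 5.0 points; OR = (16/104)/(10/110) = 1.69.

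After k abstainers leave an arm with a abstainers, its rate is (a − k)/(120 − k). Differences are computed before rounding:

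| k | Removed from Actify only | Removed from QuitGuide only |
|---|---|---|
| 2 | 14/118 − 10/120 = 3.5 points, OR 1.48 | 16/120 − 8/118 = 6.6 points, OR 2.12 |
| 4 | 12/116 − 10/120 = 2.0 points, OR 1.27 | 16/120 − 6/116 = 8.2 points, OR 2.82 |
| 6 | 10/114 − 10/120 = 0.4 points, OR 1.06 | 16/120 − 4/114 = 9.8 points, OR 4.23 |

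**When there is little or no bias**

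- Removing 4 non-abstainers from each arm: 16/116 − 10/116 = 5.2 points, OR 1.70.
- Removing the same share of abstainers from both arms leaves the unadjusted odds ratio unchanged. At 25%, (12/104)/(7.5/110) = 1.69. The absolute difference does shrink if there is a true effect: 12/116 − 7.5/117.5 = 4.0 points.
- With a true 10% rate in both arms, removing the same share (10%, 25% or 50%) from each gave a mean bias of 0.0 points and two-sided rejection of about 0.05 (200,000 simulated trials, pooled z test).

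**One-sided loss under the null.** If a share q of one arm's abstainers is dropped, that arm's expected rate is p(1 − q)/(1 − pq). With p = 0.10 and q = 0.25 (about 3 people) this is 0.075/0.975 = 7.7%, a bias of 2.3 points. Simulated bias was 0.9, 2.3 and 4.7 points for q = 10%, 25% and 50%, with rejection rates of 0.057, 0.094 and 0.269.

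**Satisfaction illustration.** With 89% retention (section 7.4), 120 × 0.89 ≈ 107 responders per arm. Removing k records lying d SD below the mean shifts that arm's mean by kd/(107 − k). For k = 5 and d = 1 to 2 this is 5/102 to 10/102, or 0.05 to 0.10 SD, against a standard error of √(2/107) = 0.14 SD for the arm difference.

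**The case against.** The case for leaving the text alone has real substance. Adjudication comes before outcome analysis, and step 8 asks for evidence in the participant's favour as well as against. Fraud control matters in a remote trial paying up to $124 (section 7.5), and removing genuine fraud reduces error. Exclusions applied alike in both arms leave the odds ratio intact. All of this stands. It does not supply masking, and it does not let a reader check whether exclusions were in fact alike in both arms.

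A reader might infer several stronger claims that the documents do not support:

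- **That straightlining removes very satisfied users.** Straightlining is an example of what to check in records already flagged for incoherent open text. It is neither the trigger nor a removal rule, so a satisfied user who writes coherently is not flagged by step 7.
- **That only survey responders can be flagged.** Baseline text is also reviewed, and the IP and address checks need no follow-up survey. Only the follow-up half of step 7 and the flag for "inconsistency between outcome surveys and screening/baseline surveys in date of birth" depend on a returned survey.
- **That every post-enrolment exclusion is a judgement on outcomes.** Step 6 and DSMP section 4.2.3 give identity-based examples.
- **That the team is unmasked, or that the process favours Actify.** Masking is unstated, which is not the same as absent. The illustration moves the estimate in either direction.

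**Conclusion.** The point holds in a narrow form. For step 8 the plan specifies no masking to arm or to individual endpoint answers, and no analysis retains the people excluded. Followed as written, the procedure permits discretionary exclusions after randomisation that depend on arm or outcome; it does not show that they will.

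The size cannot be estimated, because the number of exclusions is not given and bias requires that they differ by arm in relation to outcome. The shift from 5.0 points to 2.0 or 8.2 illustrates sensitivity and is not a forecast. It assumes the earlier pilot's quit rates, all 120 per arm in the analysis, and four abstainers lost from one arm only. Numbers in the modified intent-to-treat set may be smaller.

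This is a cheap improvement to the procedure, not a fault that undermines the trial. No stated figure changes.

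**What to change.** Amend step 8 of Appendix B and add matching text to section 14.2 and DSMP section 7.2:

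1. Adjudicators work from an extract without arm, smoking outcomes, satisfaction, BADS and PHQ-8 answers, or text that identifies the app. Someone outside the adjudication reads the open text and passes on incoherence and straightlining as yes/no flags. The notes for and against validity follow the same restriction.
2. Each decision is recorded and signed off before arm codes are merged.
3. Exclusions are reported by arm, with reasons.
4. A sensitivity analysis of the acceptability and abstinence endpoints retains everyone excluded under step 8.

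The cost is the work of preparing the masked extract and one extra table. Answer-pattern evidence need not be barred. Doing so would also leave some fraudulent records in, and passing the evidence on as flags keeps it usable.
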